12.3 Analysis Sets

12.3.1 Full Analysis Set

The full analysis set (FAS) will consist of all subjects who satisfy the following criteria:

- Randomised to either of the two treatment groups
- The administration of study treatment was started

The FAS data set will be analysed based on the randomised treatment arm.

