3. ANALYSIS POPULATIONS

3.1. Population Definitions

The following subject populations will be evaluated and used for presentation and analysis of the data:

Screened population

The screened population will consist of all subjects who signed an informed consent form.

All Randomised

The All Randomised set will consist of all subjects randomised to either of the two treatment groups. The All Randomised set will be analysed based on the randomised treatment arm.

Full Analysis Set

The Full Analysis Set (FAS) will consist of all subjects who satisfy the following criteria:

- Randomised to either of the two treatment groups, and
- The administration of study drug was started.
- At least one post-baseline visit (including calls), death or hospitalisation or subjects without post-baseline assessment who withdrew from the study after but not on the randomisation date.

Additionally, subjects with protocol deviation concerning inclusion criteria no. 5 (*Subject (or legally acceptable representative) has provided the appropriate written informed consent. Subject must provide written informed consent before any study-specific procedures are performed.*) will be excluded from FAS.

Subjects in the FAS will be analysed based on their randomised treatment arm.

Per-Protocol Set

The Per-Protocol (PP) analysis set will consist of all subjects in the FAS who had no major protocol violations (see Appendix I).

Safety Set

The Safety (SAF) analysis set will consist of all randomised subjects for whom the administration of study drug has started. Subjects will be analysed according to the treatment received.

The analysis sets to be used for analyses are described in the table below.

Table 2 Analysis Sets

Analyses	Screened population	All Randomised	FAS	PP	SAF
Subject disposition	✓	✓			
Protocol deviations/violations		✓			
Demographics			✓	✓	✓
Baseline characteristics (prior, concomitant and newly started medications, medical history including surgical history and procedures)			✓	✓	✓
Prior medications, concomitant, newly started medications			✓		✓
Medical History and history of cardiovascular factors.			✓	✓	✓
Compliance and exposure					✓
Primary endpoint			✓	✓	
Secondary endpoints			✓	✓	
Other endpoints			✓	✓	
KCCQ-12			✓	✓	
EQ-5D			✓	✓	
AEs, SAEs, and special situations					✓
Event Adjudications					✓
Laboratory parameters					✓
ECGs					✓
Vital Signs					✓

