3.2. Protocol Deviations/Violations

The sponsor, or designee, will be responsible for producing the final protocol deviation/violation file (formatted as an Excel file or SAS dataset), in collaboration with Cytel and the data monitoring group as applicable; this file will include a description of each protocol deviation/violation, and will clearly identify whether or not each violation warrants exclusion from a population. This file will be finalized prior to hard database lock.

Protocol deviations will be reported in a data listing for all subjects in the All randomised.

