4. STATISTICAL METHODS

4.1. Sample Size Justification

The recurrent HF hospitalisation and CV death rates in the control group were extrapolated as 0.9 events/year using the data from the EVEREST study [3] and as 0.61 events/year using the data from the ESC-HF study [4]. For this study, it is anticipated that approximately 35% of subjects will sustain either a CV death or at least one HF hospitalisation. It is also anticipated that 12% of subjects will sustain a CV death. Assuming that 50% of subjects who sustain a CV death will not undergo any prior HF hospitalisation and estimating the average number of HF hospitalisations per subject with at least one HF hospitalisation as 2, the number of events per 100 years of follow-up has been estimated as follows: 12 CV deaths + 2*(35-6) HF hospitalisations, which equates to approximately 70 events/100 years of follow-up for HF hospitalisations and CV death.

Concerning the event rate ratio, it is assumed that there will be a 30% reduction in HF hospitalisations for subjects allocated to FCM and that CV death rates will be similar between the FCM and placebo groups. It is therefore assumed that the rate ratio between FCM and placebo for the composite of recurrent HF hospitalisations and CV deaths will be approximately 25%.

The dispersion factor used in negative binomial regression is a measure of the mean-variance. There are currently insufficient data to estimate the negative binomial dispersion. For this sample size calculation, a dispersion factor (K) of 1 was assumed.

The sample size calculation was done in the software NCSS PASS-14 [5], using the sample size formula proposed by Zhu and Lakkis 2014 [6] to compare two negative binomial rates.

Assuming a rate of recurrent HF hospitalisation or CV death of 0.7 events/year in the placebo group, a total of 1,000 subjects (500 per study drug group) would be required to demonstrate a statistically significant rate ratio of 0.75 (i.e., 25% reduction of recurrent hospitalisations or deaths between the FCM and placebo groups) with a power of 80% and a 2-sided alpha of 0.05. Taking into account an expected 9% loss to follow-up, a sample size of 1,100 subjects (550 per treatment group) is planned.

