5. CHANGES TO PLANNED ANALYSES

Stratification factor age was used as a categorical variable for randomisation. For adjustments by covariates age will be used as a continuous variable for better precision.

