4	Subject received incorrect treatment allocation	PDIMP04	Major	None
5	Subject received treatment but failed to attend any post-baseline visit or assessment	PDIMP05	Major	Excluded from the analyses (FAS and PP)
6	Subject received study treatment not according to the administration guidelines (including undiluted bolus IV injection, duration of injection, using blinding measures as a black syringe or a curtain)	PDIMP06	Major	None
7	Subjects with IMP administered by someone other than assigned unblinded study staff	PDIMP07	Major	None
8	Subjects with events that led to unblinding of the study treatment without an emergency situation	PDIMP08	Major	Individual cases with potential impact on the primary endpoint might be excluded from PP (case review prior unblinding required)
9	Subjects with dosing of IMP not at the time point of randomization prior discharge, or randomization not done at last day of hospital discharge	PDIMP09	Major	Individual cases with potential impact on the primary endpoint might be excluded from PP (case review prior unblinding required)
10	Deviations on IMP handling like, shipment destruction prior IMP reconciliation is made or IMP storage	PDIMP10	Minor	None
11	Subjects with administration of expired IMP or IMP with deviations in the temperature log	PDIMP11	Major	Excluded from PP
12	Subject took study treatment after intake of forbidden Concomitant medication	PDIMP12	Major	Individual cases with potential impact on the primary endpoint might be excluded from PP (case review prior unblinding required)
	Other			

	Standard name of the deviation	Deviation code	Major/Potentially Critical	Statistical Assessment of the deviations
1	Unreported SAE detected by oversight activities like source data verification (not reported within 24 hours)	PDOTH01	Major	None
2	Unreported Special Situations detected by oversight activities like source data verification	PDOTH02	Minor	None
3	Entries in EDC or Source data either not available or incomplete for SDV in a timely manner	PDOTH03	Minor	None
Withdrawal from study treatment/follow ups				
1	Subject withdrew from follow up but information was collected after withdrawal consent	PDWITH01	Major	Individual cases with potential impact on the primary endpoint might be excluded from PP (case review prior unblinding required)

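### Appendix I (PDIMP05) drops from the full analysis set treated subjects whom SAP 3.1 and protocol 12.3.1 keep, and no rule says which prevails

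*SAP*

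**What the plan says.** Three places define who is in the FAS, the set used for the primary analysis (SAP 4.6).

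- Protocol 12.3.1 has two conditions: the subject was randomised, and "The administration of study treatment was started". Nothing after baseline is required.
- SAP 3.1 adds a third condition, met by "At least one post-baseline visit (including calls), death or hospitalisation" or by belonging to the "subjects without post-baseline assessment who withdrew from the study after but not on the randomisation date". It also removes subjects with the consent deviation (inclusion criterion 5).
- SAP Appendix I, Investigational Medicinal Product, PDIMP05 covers "Subject received treatment but failed to attend any post-baseline visit or assessment". It is graded Major and the assessment is exclusion from FAS and PP. It has no exception for withdrawal, death or hospitalisation.

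SAP 3.2 leaves the outcome to a deviation file, final before hard database lock, that "will clearly identify whether or not each violation warrants exclusion from a population". It does not say whether 3.1 or Appendix I prevails. SAP 1.2.2 undertakes to set out differences from the protocol's planned analyses, but section 5 records only one: "For adjustments by covariates age will be used as a continuous variable for better precision".

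**The concern.** A treated subject who had no post-baseline assessment and withdrew after the day of randomisation is in the FAS under SAP 3.1 and out under PDIMP05. Two programmers could each follow the SAP and derive different primary analysis sets.

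PDIMP05 also excludes on what happens after randomisation, which is what a full analysis set is meant to avoid. Read literally, it reaches subjects who died before any visit or call, or who were hospitalised and never attended afterwards. CV deaths and HF hospitalisations are primary endpoint events. Protocol 5.4.2 asks sites to keep following for outcomes those who stop attending and have not withdrawn consent, so the rule could discard events that the protocol takes care to collect.

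SAP 3.1 repeats one of the two Appendix I exclusions from the FAS (consent) but not the other (PDIMP05). Whether PDIMP05 applies therefore depends on which page is read.

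**Working it through.** The plan gives no figure for this point, so the first step compares the rules.

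**Step 1: treated subjects under each rule (FAS membership; consent deviation aside)**

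| Treated subject | Protocol 12.3.1 | SAP 3.1 | PDIMP05 |
|---|---|---|---|
| A. At least one post-baseline visit or call | in | in | in |
| B. Died or was hospitalised, never attended a visit or call | in | in | out if read literally |
| C. No assessment, withdrew after the randomisation date | in | in | out |
| D. No assessment, withdrew on the randomisation date | in | out | out |
| E. No assessment; no withdrawal, death or hospitalisation recorded | in | out | out |

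Row C is a contradiction on the wording. Row B is one unless a death or hospitalisation counts as an assessment. In rows D and E the two SAP rules agree but are narrower than the protocol, and section 5 does not list this.

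**Step 2: size of row C**

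The documents give no count. A subject who left by day 17, the end of the Week 2 call window (2 weeks ± 3 days, protocol Table 2), would contribute at most 17/365.25 = 0.05 patient-years. Planned follow-up is 1,100 × 11/12 = 1,008 patient-years, using the 11-month mean in the protocol synopsis.

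**Step 3: size of row B, CV deaths only, literal reading**

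Inputs: 1,100 subjects and the SAP 4.1 statement "It is also anticipated that 12% of subjects will sustain a CV death". Assumptions: the 12% applies to 52 weeks (364 days), and the early hazard is *m* times a constant average.

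CV deaths by day *d* = 1,100 × (1 − 0.88^(m·d/364))

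| | m = 1 | m = 2 | m = 3 |
|---|---|---|---|
| Day 11 | 4.2 | 8.5 | 12.7 |
| Day 14 | 5.4 | 10.8 | 16.1 |
| Day 17 | 6.5 | 13.1 | 19.5 |

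**Step 4: set against the planned totals**

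- Planned CV deaths: 0.12 × 1,100 = 132. Share by day 14 at m = 1: 5.4/132 = 4.1%.
- Planned primary events: 0.7 × 550 × 11/12 = 352.9 on placebo and 0.525 × 550 × 11/12 = 264.7 on FCM, total 617.6. Share: 5.4/617.6 = 0.9%. At the top of the range, 19.5/617.6 = 3.2%.
- Rate ratio if the lost deaths split evenly, in line with the similar CV death rates assumed in SAP 4.1: (264.7 − 2.7)/(352.9 − 2.7) = 262.0/350.2 = 0.748, against the planned 0.75. With 19.5 lost: (264.7 − 9.75)/(352.9 − 9.75) = 0.743.
- 30-day CV mortality at m = 1: 1,100 × (1 − 0.88^(30/364)) = 11.5 deaths expected, of which 5.4/11.5 = 47% fall by day 14.

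**The case against.** The best defence is that PDIMP05 is a deviation code and speaks of failing to attend. Protocol 5.4.2 allows withdrawal at any time, and the first scheduled contact after the in-hospital dose is the Week 2 call. A subject who withdraws or dies before then has missed nothing scheduled and need not be coded. PDIMP05 would then catch only row E (and perhaps D), whom SAP 3.1 excludes anyway. This may well be the intention, but it is written nowhere. Protocol 9.2.2.5 asks withdrawing subjects to return for an assessment, so one who declines could be coded as not attending.

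The second defence is that little turns on it. That stands: row C adds no recorded events and almost no follow-up, and all the event-based figures depend on the literal reading of row B.

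Some stronger readings are tempting but unsupported:

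- *The 9% gives the number of early withdrawals.* SAP 4.1 ("Taking into account an expected 9% loss to follow-up") does not separate withdrawal from simple loss to follow-up, and a subject simply lost without any contact is out under both SAP rules.
- *About 5 CV deaths is a maximum.* It holds only at constant hazard. Protocol 1.1 describes poor outcomes in the months after discharge, and a subject could miss both the Week 2 and Week 4 calls and then die. In the other direction, some early deaths will have had an unscheduled assessment.
- *The PP set is undefined.* SAP 3.1, taken alone, bars every Major deviation from PP, although Appendix I assesses ten Major rows as needing no action and sends 29 to case review. But 3.1 refers to Appendix I, which has a statistical assessment column, and the SAP 3.2 file records each exclusion. What remains is wording.

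**Conclusion.** The conflict is real and should be settled before unblinding. On the wording, PDIMP05 contradicts SAP 3.1 for treated subjects who withdrew after the randomisation date without an assessment. On a literal reading it also contradicts 3.1 for those who died or were hospitalised and never attended. The protocol keeps both groups, and nothing in SAP 3.2 or section 5 resolves the matter.

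The likely effect on the primary result is small. The number of withdrawals is unknown. The CV deaths at risk are about 5 by day 14 at constant hazard, or about 4 to 20 over days 11 to 17 with an early hazard 1 to 3 times average; the multipliers are assumptions. The 30-day endpoints are more exposed, because close to half of their CV deaths could fall before the first scheduled call.

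A reader might infer that the rule favours one arm. The documents give no basis for that; the case for change is that an exclusion from the primary set should not depend on post-randomisation attendance or on which page is followed.

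**What to change.** Before unblinding:

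1. Limit the FAS exclusion in PDIMP05 to subjects who do not meet the SAP 3.1 FAS criteria. Treated subjects who died, were hospitalised, or withdrew after the randomisation date then stay in the FAS.
2. State the same limit for PP, so that PDIMP05 does not remove a subject only because of an early death.
3. List in section 5 how the 3.1 FAS differs from protocol 12.3.1: the added third condition and the consent exclusion.

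Optional, wording only: say in 3.1 that the statistical assessment column of Appendix I governs PP membership, and replace the reference to an ITT population in PDEXC21 with a set that 3.1 defines.

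The cost is a few lines of SAP text and a re-derivation of the deviation file. No new data are needed.

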Appendix II: Calculation of planned dose

Protocol Number	Planned Dose
1, 1.1, 1.2 and country NE The Netherlands, Singapore, Spain	
"Hemoglobin in g/dL" < 8: No dose "Hemoglobin in g/dL" > 15: No dose
 
Visit 2 If "Serum pregnancy test" = "Positive": No dose 8 ≤ "Hemoglobin in g/dL" ≤ 14: 2 Kits 14 < "Hemoglobin in g/dL" ≤ 15: 1 Kit
 
Visit 3 If "Serum pregnancy test" = "Positive": No dose "Weight in kg" < 70 and 8 ≤ "Hemoglobin in g/dL" < 10 and "ID persists" : 1 Kit "Weight in kg" < 70 and 10 ≤ "Hemoglobin in g/dL" ≤ 14 : No dose "Weight in kg" ≥ 70 and 8 ≤ "Hemoglobin in g/dL" < 10 and "ID persists" : 2 Kits "Weight in kg" ≥ 70 and 10 ≤ "Hemoglobin in g/dL" ≤ 14 and "ID persists" : 1 Kit "Hemoglobin in g/dL" > 14 : No dose
 
Visit 4 and Visit 5 If "Serum pregnancy test" = "Positive": No dose "ID persists" : 1 Kit

2, 3 and country NE The Netherlands, Singapore, Spain	
"Hemoglobin in g/dL" < 8: No dose "Hemoglobin in g/dL" > 15: No dose
 
Visit 2 If "Serum pregnancy test" = "Positive": No dose 8 ≤ "Hemoglobin (from screening) in g/dL" ≤ 14: 2 Kits 14 < "Hemoglobin (from screening) in g/dL" ≤ 15: 1 Kit
 
Visit 3 If "Serum pregnancy test" = "Positive": No dose "Weight in kg" < 70 and 8 ≤ "Hemoglobin (from screening) in g/dL" < 10 : 1 Kit "Weight in kg" < 70 and 10 ≤ "Hemoglobin (from screening) in g/dL" ≤ 14 : No dose "Weight in kg" ≥ 70 and 8 ≤ "Hemoglobin (from screening) in g/dL" < 10: 2 Kits "Weight in kg" ≥ 70 and 10 ≤ "Hemoglobin (from screening) in g/dL" ≤ 14 : 1 Kit "Hemoglobin in g/dL" > 14 : No dose
 
Visit 4 and Visit 5 If "Serum pregnancy test" = "Positive": No dose "ID persists" : 1 Kit

Protocol Number	Planned Dose
If country = The Netherlands, Singapore, Spain	Same calculation as described above applies depending on protocol version. However, replace lower threshold for Hemoglobin by 10 g/dL instead of 8 g/dL.

Note:

ID is defined as serum ferritin <100 ng/mL, or $100 \text{ ng/mL} \leq \text{serum ferritin} \leq 299 \text{ ng/mL}$ if transferrin saturation (TSAT) is <20%. The laboratory and vital sign values closest to the injection date and time (\leq) is used. In case no injection was done, the value closest to the visit date will be used.

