Table 1 Study Treatment Dosing Regimen

Treatment Visit	Total mL FCM or Saline				
	Weight <70 kg		Weight ≥70 kg		Any Weight
	8 g/dL ⁽¹⁾ ≤ Hb <10 g/dL	10 g/dL ≤ Hb ≤14 g/dL	8 g/dL ⁽¹⁾ ≤ Hb <10 g/dL	10 g/dL ≤ Hb ≤14 g/dL	14 g/dL < Hb ≤15 g/dL
Visit 2 (Week 0)	2x10 mL				1x10 mL
Visit 3 ⁽²⁾ (Week 6)	1x10 mL	No dose	2x10 mL	1x10 mL	No dose
Visit 4, Visit 5 (Week 12, Week 24)	1x10 mL (only if ID persists)				

1 Following section in italics is applicable for The Netherlands, Spain and Singapore only (**NL, ES and SG only**) *The lower threshold of Hb values for subject eligibility prior to enrolment into the study is set to 10 g/dL. Subjects enrolled in the study in NL, ES and SG only with Hb levels that are falling below the threshold of 10 g/dL during the study will need to be withdrawn from further study treatment dosing.*

2 Dosing at Week 6 (Visit 3) will be based on the iron need upon screening Hb and weight values and only be done in subjects for whom Hb at Week 6 (Visit 3) ≤15 g/dL.

Notes: FCM=Ferric carboxymaltose; Hb=Haemoglobin; ID=Iron deficiency.

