5.4 Withdrawal of Subjects

5.4.1 Withdrawal of Subjects from Study Drug

Study drug must be stopped if the subject experiences any kind of hypersensitivity reaction related to the study drug during administration. The subject concerned will remain under follow-up and the subsequent visits should be performed in accordance with the protocol schedule. Whether the subject should receive additional doses of study treatment will be discussed with the Medical Monitor and will be decided on a case by case basis. If study drug is stopped prematurely for any one subject, the subject concerned will not be replaced.

Subjects may be withdrawn from the study drug if in the opinion of the Medical Monitor or the Investigator there would be a risk to the subject's safety if they received any further dose of study drug.

Following section in italics is applicable for The Netherlands, Spain and Singapore only (**NL, ES and SG only**):

Subjects enrolled in the study with Hb levels that are falling below the threshold of 10 g/dL during the study will need to be withdrawn from further study treatment dosing.

If study treatment is stopped prematurely for a subject, follow-up for the subject concerned should continue in accordance with the protocol schedule. The discontinuation of study treatment is mandatory in circumstances that therapies or treatments listed in Section 7.7.2 as restricted need to be applied to the subjects for general health reasons. Discontinuation of study treatment is also mandatory in the case a subject enrolled into the study is getting pregnant (see Section 10.3.3 for reporting instructions).

The reason for study-drug discontinuation and the date must be recorded on the appropriate page of the eCRF. The follow-up of these subjects should continue in accordance with the protocol schedule.

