4.8.1. Treatment Exposure and Compliance

Time on study (follow-up) in weeks and subject-years on study as defined in sections 4.2.14 and 4.2.18 will be summarised as continuous variables. Time on study drug as defined in section 4.2.15 will also be summarised.

Treatment Exposure

The number of injections of study drug per subject will be summarised as a categorical variable (1, 2, 3, 4). The total amount of study drug given and planned (see Table 6 and Table 7) across

visits (mL) will be calculated for each subject, and will be summarised by treatment group. Summary statistics for the doses received (in mL and in mg) at each visit be also presented.

The total amount of study drug and the doses received at each visit in mL and mg will also be summarised as a continuous variable.

Treatment Compliance

The planned dose will be derived based on the protocol number, protocol consent and re-consent dates, serum pregnancy test result, weight, Hb levels, and ID status as per Table 6 and Table 7 below. Table 7 will apply only for subjects who consented to protocol 2 or 3 or if the subject re-consented to protocol 2 and the injection date is on or after the protocol re-consent date. ID is defined as serum ferritin <100 ng/mL, or $100 \text{ ng/mL} \leq \text{serum ferritin} \leq 299 \text{ ng/mL}$ if transferrin saturation (TSAT) is <20%. The laboratory and vital sign values closest to the injection date and time (\leq) will be used. In case no injection was done, the value closest to the visit date will be used.

For the protocol 1, the first dose of study treatment is administered for all randomised subjects on the same day as randomisation – i.e., at Visit 2 while the subject is still hospitalised for the Index hospitalisation. The subsequent administrations of study treatment are done as part of the outpatient clinic visits at Week 6 (Visit 3), and at Weeks 12 (Visit 4) and 24 (Visit 5) only for subjects in whom ID persists and for whom $\text{Hb} \geq 8 \text{ g/dL}$ and $\leq 15 \text{ g/dL}$. The serum pregnancy test must also be negative for the respective visit for females of childbearing potential.

The dosing regimen for protocol 1.2 is similar to the one from protocol 1 except for the subjects from The Netherlands (NL). For NL subjects, the lower threshold of Hb values is set to 10 g/dL.

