For the protocol 2 and 3, dosing at Week 6 (Visit 3) is based on the iron need upon screening Hb and weight values to replete iron as described in Table 7 and only be done in subjects for whom $\text{Hb} \leq 15 \text{ g/dL}$. Maintenance dosing at Weeks 12 (Visit 4) and 24 (Visit 5) is only for subjects in whom ID persists and for whom $\text{Hb} \geq 8 \text{ g/dL}^*$ and $\leq 15 \text{ g/dL}$ at those visits. The serum pregnancy test must also be negative for the respective visit for females of childbearing potential.

* Following section in italics is applicable for The Netherlands, Spain and Singapore only (**NL, ES and SG only**):

The lower threshold of Hb values is set to 10 g/dL.

Table 6 Study drug Dosing Regimen Protocol 1

Treatment Visit	Total mL FCM or Saline				
	Weight <70 kg		Weight ≥70 kg		Any Weight
	8 g/dL ≤ Hb < 10 g/dL	10 g/dL ≤ Hb ≤ 14 g/dL	8 g/dL ≤ Hb < 10 g/dL	10 g/dL ≤ Hb ≤ 14 g/dL	
Visit 2 (Week 0)	2x10 mL				1x10 mL
Visit 3 (Week 6)	1x10 mL (only if ID persists)	No dose	2x10 mL (only if ID persists)	1x10 mL (only if ID persists)	No dose
Visit 4, Visit 5 (Week 12, Week 24)	1x10 mL (only if ID persists)				

Notes: FCM=Ferric carboxymaltose; Hb=Haemoglobin; ID=Iron deficiency.

Table 7 Study drug Dosing Regimen Protocols 2, 3

Treatment Visit	Total mL FCM or Saline				
	Weight <70 kg		Weight ≥70 kg		Any Weight
	8 g/dL ⁽¹⁾ ≤ Hb <10 g/dL	10 g/dL ≤ Hb ≤14 g/dL	8 g/dL ⁽¹⁾ ≤ Hb <10 g/dL	10 g/dL ≤ Hb ≤14 g/dL	
Visit 2 (Week 0)	2x10 mL				1x10 mL
Visit 3 ⁽²⁾ (Week 6)	1x10 mL	No dose	2x10 mL	1x10 mL	No dose
Visit 4, Visit 5 (Week 12, Week 24)	1x10 mL (only if ID persists)				

1 Following section in italics is applicable for The Netherlands, Spain and Singapore only (NL, ES and SG only): *The lower threshold of Hb values for subject eligibility prior to enrolment into the study is set to 10 g/dL. Subjects enrolled in the study in NL, ES and SG only with Hb levels that are falling below the threshold of 10 g/dL during the study will need to be withdrawn from further study treatment dosing.*

2 Dosing at Week 6 (Visit 3) will be based on the iron need upon screening Hb and weight values and only be done in subjects for whom Hb at Week 6 (Visit 3) ≤15 g/dL.

Notes: FCM=Ferric carboxymaltose; Hb=Haemoglobin; ID=Iron deficiency.

The algorithm to calculate the planned dose is described in Appendix II.

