The calculated planned dose and the dose administered as collected in the eCRF will be used to calculate the dosing information (dose given as planned, reduced, increased). It will be summarised for each treatment visit (Baseline, Visit 3 [Week 6], Visit 4 [Week 12], and Visit 5 [Week 24]).

The total amount of study drug given during the study will be calculated for each subject and will be compared to the amount expected to be given for each subject based on weight, Hb levels, and ID status. Treatment compliance will be calculated for each subject and summarised by treatment group and summarised as continuous and categorical variable (<80, 80-120, > 120 as categories)

- Total amount = total volume administered in mL over all visits.
- Expected amount = total volume in mL that should have been administered as described in Table 6.
- Compliance rate = (total amount/expected amount)*100.

Treatment compliance and drug concentration information will also be reported in data listings.

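### For subjects under protocol versions 2 and 3, the SAP's expected-dose rules depart from its own Table 7, so some correctly dosed subjects are scored as under- or over-dosed

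*SAP*

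**What the plan says.** **Which regimen applies.** SAP 4.8.1 derives the planned dose from Tables 6 and 7 and then separates them: "Table 7 will apply only for subjects who consented to protocol 2 or 3", with a provision for subjects who re-consented to version 2. Under those versions, "dosing at Week 6 (Visit 3) is based on the iron need upon screening Hb and weight values". Protocol Table 1 note 2 says the same and adds one check on current Hb: the Week 6 dose will "only be done in subjects for whom Hb at Week 6 (Visit 3) ≤15 g/dL". Neither source makes the Week 6 dose depend on ID persisting. Table 6, the version 1 regimen, does; one of its Week 6 cells reads "2x10 mL (only if ID persists".

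**Expected amount.** The compliance denominator in SAP 4.8.1 is defined thus: "Expected amount = total volume in mL that should have been administered as described in Table 6". Compliance is the volume given divided by this amount, times 100, reported in categories <80, 80–120 and >120.

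**The 10 g/dL rule.** Protocol 5.4.1 requires that subjects in the Netherlands, Spain and Singapore with Hb "falling below the threshold of 10 g/dL during the study will need to be withdrawn from further study treatment dosing". SAP Table 7 note 1 carries the same rule ("Subjects enrolled in the study in NL, ES and SG only with Hb levels that are falling below the threshold of 10 g/dL"). For these countries Appendix II instructs only to "replace lower threshold for Hemoglobin by 10 g/dL instead of 8 g/dL".

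**Visit 3 inputs in Appendix II (versions 2 and 3).** Four lines mark Hb as coming from screening. Weight in those lines has no such label, and neither has the last line, which gives no dose when Hb exceeds 14. The Note under the table takes laboratory and vital-sign values closest to the injection or, if there was no injection, closest to the visit date.

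**The concern.** The planned and expected doses are the yardstick for two outputs: the by-visit summary of doses given as planned, reduced or increased, and the compliance rate. If the yardstick differs from the regimen that sites were told to follow, correct dosing is reported as a departure. The reverse can also happen: a subject wrongly re-dosed after a mandatory stop would be counted as dosed as planned. A reader who uses these tables to judge how well the regimen was delivered would be misled in either direction.

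**Working it through.** The plan states no compliance figure, so there is nothing to reproduce. The check takes hypothetical subjects under versions 2 or 3, doses them exactly as protocol Table 1, SAP Table 7 and protocol 5.4.1 require, and scores them by the SAP's rules.

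Formula (SAP 4.8.1): compliance = 100 × mL given / mL expected. Volumes come from Tables 6 and 7: 20 mL at Week 0 for Hb up to 14 g/dL; 10 mL at Week 6 for 70 kg or more with Hb 10–14, none below 70 kg; 10 mL at each of Weeks 12 and 24 if due.

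**Control.** 80 kg, screening Hb 12, ID still present at Week 6, no maintenance dose: 30/30 = 100% under Table 6, Table 7 and Appendix II alike.

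**1. Expected amount from Table 6, as the line is written.** 80 kg, screening Hb 12, ID resolved at Week 6. Table 7 gives 20 + 10 = 30 mL; Table 6 expects 20 + 0 = 20 mL.

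- No maintenance dose: 30/20 = 150%
- One maintenance dose: 40/30 = 133%
- Two maintenance doses: 50/40 = 125%

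Appendix II plans the same 10 mL at Week 6. So the by-visit table would call the dose as planned while the compliance table puts the subject above 120.

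**2. The stop in the Netherlands, Spain and Singapore (denominator: Appendix II).** Screening Hb 10–14; Hb falls below 10 and later returns to 10 or more with ID present.

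| Course | Given | Appendix II plans | Compliance |
|---|---|---|---|
| Fall at Week 6; ID at Weeks 12 and 24 | 20 | 20+0+10+10 = 40 | 50% |
| Fall at Week 6; ID at one later visit | 20 | 20+0+10 = 30 | 67% |
| Fall at Week 12, below 70 kg; ID at Week 24 | 20 | 20+0+0+10 = 30 | 67% |
| Fall at Week 12, 70 kg or more; ID at Week 24 | 30 | 20+10+0+10 = 40 | 75% |

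If the first subject were wrongly given both later doses, the score would be 40/40 = 100%.

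**3. Visit 3 weight (denominator: Appendix II).** Screening Hb 12; the Note selects Week 6 weight.

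- 72 kg at baseline, 68 kg at Week 6: given 20 + 10 = 30, planned 20, so 150%. With two maintenance doses, 50/40 = 125%.
- 68 kg at baseline, 71 kg at Week 6: given 20, planned 20 + 10 = 30, so 67%. With two maintenance doses, 40/50 = 80%, just inside the middle category; the Week 6 dose would still be shown as reduced.

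**After the fix.** With Table 7 as denominator, baseline weight, screening Hb and the stop carried forward, given and expected volumes agree and each of these correctly dosed subjects scores 100%.

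**The case against.** **Two denominators.** The percentages under 1 use Table 6 and those under 2 and 3 use Appendix II, and both cannot be the denominator. This is right, and a reader should not infer that all the figures would appear together. If Appendix II is the denominator, item 1 disappears; if the Table 6 line is literal, the percentages under 2 and 3 are not the SAP's. The by-visit summary uses the calculated planned dose, hence Appendix II, so items 2 and 3 distort that table whichever denominator is chosen.

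**Stale cross-reference.** The rest of 4.8.1 names both tables, and Appendix II has no ID condition at Visit 3 for versions 2 and 3. The Table 6 citation is probably a leftover. It is still the only definition of the compliance denominator, and it is wrong as written.

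**Withdrawal as a convention.** Appendix II carries no discontinuation forward, whether for hypersensitivity, prohibited therapy or pregnancy, so a planned dose that continues after a stop could be a general choice. This has some force. But the stop in the three countries is triggered by Hb, one of the stated inputs, and is a note to the regimen table itself.

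**The Hb > 14 line.** One could read it as current Hb, cancelling the dose of a subject with screening Hb 13.0 and Week 6 Hb 14.5. The documents favour a dropped label. Only a screening reading completes the algorithm: otherwise screening Hb 14.5 with Week 6 Hb 13 matches no Visit 3 line. No size is claimed for it.

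**Week 6 Hb below 8 g/dL.** Outside the three countries, Appendix II cancels the Week 6 dose here, although the protocol sets only the upper limit at that visit. This is a mismatch in wording, but it should seldom arise, since transfusion or a safety decision stops dosing. Correcting it would make the SAP plan iron at a level that bars entry and maintenance dosing. It is no part of the recommendation.

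**Conclusion.** The point holds as a minor inconsistency. For versions 2 and 3, the expected-amount line and Appendix II do not reproduce Table 7, protocol Table 1 or protocol 5.4.1. A correctly dosed subject can score 125–150% under the Table 6 line. On the Appendix II denominator the range is 50–75% after a correct stop, and 150% or 67% after crossing 70 kg with no maintenance dose.

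These are per-subject results for constructed cases. They assume that the SAP is programmed as written and that no other dosing error occurs. The number of subjects affected cannot be derived from the documents. Item 2 needs one of 3 of the 15 countries in SAP Table 4, a fall at Week 6 or 12, and then recovery with ID.

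A reader might infer that the per-protocol set is also wrong, because Appendix I excludes subjects for incorrect or missed doses. The documents do not support that: SAP 3.2 takes exclusions from a separate deviation file, and nothing ties that file to Appendix II or to the 80–120 category. SAP Table 2 places compliance and exposure in the Safety Set only. The Full Analysis Set primary analysis does not use them.

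**What to change.** Change the SAP only:

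1. In 4.8.1, state that the expected amount is the Appendix II planned dose summed over visits, using Table 6 or Table 7 according to protocol version.
2. In Appendix II, for the Netherlands, Spain and Singapore under versions 2 and 3, set the planned dose to zero at the first post-baseline visit with Hb below 10 g/dL and at every later visit.
3. In the versions 2 and 3 block, label Visit 3 weight as the baseline/screening value and the Hb > 14 line as screening Hb. Keep the cancellation when Week 6 Hb exceeds 15 g/dL.

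The cost is a few lines of SAP text and the matching programming. No protocol change and no new data are needed.
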